7.4.4. MPN-SAF and Total Symptom Score

The TSS for the MPN-SAF is determined at visits where the Myeloproliferative Neoplasms Symptom Assessment Form is administered. When all items are completed for a visit, the TSS is the sum of the numeric values of the 10 questions (each scored on a 0-10 scale), which includes

fatigue, concentration, early satiety, inactivity, night sweats, itching, bone pain, abdominal discomfort, weight loss, and fevers. If only 6 to 9 items are completed, the TSS for the visit is the average completed TSS item score multiplied by 10. If 5 or fewer items are completed on the MPN-SAF, the TSS is missing for that visit ([Emanuel et al 2012](#)).

The percentage change at Week 4, 8, 12, 16, 20, and 24 will be calculated using the formula

$$\% \text{ change} = 100 \times (\text{Week xx total score} - \text{baseline total score}) / \text{baseline total score}$$

and will be summarized with descriptive statistics (mean, standard deviation, etc).

Summaries for the 10 individual scores will be provided using the same windows and formula used for the TSS.

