2.2. Study Objectives and Endpoints

Study objectives and endpoints are presented in [Table 1](#).

Table 1: Study Objectives and Endpoints

Primary Objective	Primary Endpoint
To evaluate preliminary efficacy of itacitinib on SVR from baseline at Week 24 in the 2 following cohorts of MF subjects: 
• Cohort A: in combination in subjects with ruxolitinib low dose (less than 20 mg daily).• Cohort B: as monotherapy in subjects who progressed (per revised ELN 2013 response criteria for MF) after initial reduction in spleen on ruxolitinib or discontinued for hematologic toxicities.	Change and percentage change in SVR as measured by MRI (CT scan in subjects who are not candidates for MRI or when MRI is not readily available) at Week 24 when compared with baseline.
Secondary Objectives (Cohorts A and B)	Secondary Endpoints
To evaluate preliminary safety and tolerability of itacitinib alone.	Safety and tolerability through assessment of frequency, severity, and duration of AEs; changes in clinical safety assessments; and changes in clinical laboratory parameters.
To evaluate preliminary safety and tolerability of itacitinib in combination with ruxolitinib.	Change and percentage change in SVR from baseline through Week 12 as measured by MRI (or CT scan in applicable subjects).
To evaluate preliminary efficacy of itacitinib alone or in combination with ruxolitinib on spleen length reduction from baseline at Week 12 and Week 24.	Change and percentage change in spleen length from baseline through Week 12 and Week 24 as measured by palpation.
To evaluate preliminary efficacy of itacitinib alone or in combination with ruxolitinib with respect to MF symptoms at Week 12 and Week 24.	Change and percentage change in TSS from baseline through Week 12 and Week 24 as measured by the MFSAF v2.0 symptom diary and by the MPN-SAF.
	PGIC score at each visit where the variable is measured.
To evaluate preliminary efficacy of itacitinib using IWG-MRT criteria.	Number of subjects with responses according to the 2013 IWG-MRT consensus criteria for treatment response.
To assess the PK of itacitinib and ruxolitinib.	Calculation of the PK parameters such as AUC, CL/F, C _{max} , and t _{max} along with summarization of the observed concentration data by timepoint will be performed for both ruxolitinib and itacitinib.

Table 1: Study Objectives and Endpoints (Continued)

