3.2. Control of Type I Error

The level of significance for detecting a difference from a 0% median percentage SVR in each cohort is 5% (1-sided). In other words, under the null hypothesis of subjects receiving itacitinib having a true median percentage SVR of 0%, there is a 5% chance of declaring a given cohort as having a median percentage $SVR > 0\%$. Note that this level of significance does not account for testing of multiple cohorts.

All other statistical analyses are exploratory in nature. Unless otherwise specified, all CIs provided will be at the 95% confidence level.

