5. STATISTICAL METHODOLOGY

5.1. General Methodology

Unless otherwise noted, SAS® software (SAS Institute Inc, Cary, NC; Version 9 or later) will be used for the generation of all tables, graphs, and statistical analyses. Descriptive summaries for continuous variables will include, but not be limited to, the number of observations, mean, standard deviation, median, minimum, and maximum. Descriptive summaries for categorical variables will include the number and percentage of subjects in each category.

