7.4.3. MFSAF v2.0 and Total Symptom Score

The daily TSS for MFSAF v2.0 is determined on a study day basis and is the sum of the 6 individual symptom scores as measured by the daily symptom diary excluding the score for degree of inactivity. Included items are itching, night sweats, abdominal discomfort/bloating, early satiety, pain under the ribs on left side and bone/muscle pain. If any of the 6 components of the score are missing, then the daily TSS is missing on that day. Observations with missing dates will be excluded from the analysis.

The TSS for baseline, Week 12, and Week 24 will be determined by averaging the daily TSS for the days between the start and end of windows as described in [Table 2](#). The TSS for Weeks 4, 8, 16, and 20 will be derived in a similar fashion using the first nonmissing daily TSS available between

Day ($7 \times \text{week}$)

and

Day ($7 \times \text{week}$) + 7

as the end of the window.

Table 2: Windows for Deriving Total Symptom Score for Baseline, Week 12, and Week 24

Period	Start of Window	End of Window	Missing
Baseline	7 days on or prior to end of window	Last day a daily TSS was collected between Day -7 and Day -1 (inclusive)	4 or more missing out of the 7 daily TSSs in the window; or no measurement between Day -7 and Day -1
Week 12	7 days on or prior to end of window	First day a daily TSS was collected between Day 84 and Day 90 (inclusive)	4 or more missing out of the 7 daily TSSs in the window; or no measurement between Day 84 and Day 90
Week 24	7 days on or prior to end of window	First day a daily TSS was collected between Day 168 and Day 174 (inclusive)	4 or more missing out of the 7 daily TSSs in the window; or no measurement between Day 168 and Day 174

The percentage change at Week 4, 8, 12, 16, 20, and 24 will be calculated using the formula

$$\% \text{ change} = 100 \times (\text{Week xx total score} - \text{baseline total score}) / \text{baseline total score}$$

and will be summarized with descriptive statistics (mean, standard deviation, etc).

Summaries for the 7 individual scores will be provided using the same windows used for the TSS.

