2.2 Secondary Efficacy				
2.2.1	Summary of Spleen Length Measured by Palpation by Visit	FAS		X
2.2.2.1	Summary of Total Symptom Score Using MFSAF Version 2.0 by Visit	FAS		X
2.2.2.2	Summary of Percentage Change in Total Symptom Score Using MFSAF Version 2.0 by Visit	FAS		X
2.2.2.3	Summary of Total Symptom Score Using MFSAF Version 2.0 by Visit and HMR Gene Mutation Status	FAS		X
2.2.2.4	Summary of Percentage Change in Total Symptom Score Using MFSAF Version 2.0 by Visit and HMR Gene Mutation Status	FAS		X

Table No.	Title	Population	Standard	In-Text
2.2.2.5	Summary of MFSAF Version 2.0 Components by Visit	FAS		X
2.2.3.1	Summary of Total Symptom Score Using MPN-SAF by Visit	FAS		X
2.2.3.2	Summary of Percentage Change in Total Symptom Score Using MPN-SAF by Visit	FAS		X
2.2.3.3	Summary of Total Symptom Score Using MPN-SAF by Visit and HMR Gene Mutation Status	FAS		X
2.2.3.4	Summary of Percentage Change in Total Symptom Score Using MPN-SAF by Visit and HMR Gene Mutation Status	FAS		X
2.2.3.5	Summary of MPN-SAF Components by Visit	FAS		X
2.2.4.1	Summary of PGIC by Visit	FAS		X

2.90.# AD HOC or Additional Analyses

Safety

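### SAP section 7.4.4 extends the percentage-change formula to single MPN-SAF items, where it is undefined at a baseline of 0 and unstable at 1 or 2, and does not commit to any other item summary

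*SAP*

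**What the plan says.** Section 7.4.4 defines the MPN-SAF total symptom score (TSS) as "the sum of the numeric values of the 10 questions (each scored on a 0-10 scale"), so 0 is a legitimate item score. It displays one equation, percentage change from baseline with the baseline score as denominator, and closes with "Summaries for the 10 individual scores will be provided using the same windows and formula used for the TSS".

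The parallel sentence in section 7.4.3, for the MFSAF v2.0 diary, is narrower: "Summaries for the 7 individual scores will be provided using the same windows used for the TSS". It carries over the windows but no formula.

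Appendix A lists a table titled "Summary of Percentage Change in Total Symptom Score Using MPN-SAF by Visit" (2.2.3.2). For the items it lists only "Summary of MPN-SAF Components by Visit" (2.2.3.5), without naming the quantity shown.

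Three other places bear on the point. Section 5.1 requires continuous summaries to include "the number of observations, mean, standard deviation, median, minimum, and maximum". Section 4.1.4 says missing values are not imputed unless a method is given, and no method is given for a zero baseline. Table 1 in section 2.2 names the symptom endpoint as "Change and percentage change in TSS from baseline through Week 12 and Week 24", together with PGIC; single items are not listed.

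**The concern.** A ratio to baseline can work for a 10-item total, which is 0 only if every completed item is 0. A single 0-10 item is different, because a subject without that symptom scores 0. For that subject the formula divides by zero whatever the follow-up score.

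The loss runs one way. A subject at 0 can only stay at 0 or worsen, so the omitted subjects are exactly those in whom the symptom could newly appear. Subjects at 1 or 2 stay in, but one point counts as 100% or 50%, while improvement can never go below -100%.

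What is at stake is how the item results read in the study report. A percentage-change summary describes only subjects who already had the symptom, and its mean may differ in size or sign from the change in the cohort.

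**Working it through.** The plan states no figure for the item summaries, so there is nothing to reproduce. Its power figure belongs to the primary sign test and does not enter here.

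**Which formula is meant.** Section 7.4.4 contains three TSS rules: the sum of 10 items, the average completed item score times 10, and percentage change. The first two build a total and cannot be applied to one item. Only percentage change remains, and it is the only displayed equation.

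**The formula on one item.** With baseline b and follow-up w, % change = 100 × (w − b)/b.

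- 0 to 0, 0 to 5 and 0 to 10: undefined. The absolute changes are 0, +5 and +10.
- 1 to 2: +100%. 1 to 10: +900%.
- 5 to 0 and 10 to 0: both -100%.

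**How often it would occur.** The cohort size of up to 21 is from section 3.3. The share q of subjects at 0 is an assumption. The expected number with a defined value is 21(1 − q), and the chance of at least one undefined value for an item in a cohort is 1 − (1 − q)^21.

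- q = 10%: 18.9 defined; chance 89%.
- q = 20%: 16.8 defined; chance 99%.
- q = 30%: 14.7 defined; chance above 99%.
- q = 50%: 10.5 defined; chance above 99%.

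**Effect of zero baselines (assumed data).** Of 21 subjects, z start at 0 and one third of those rise to 3. The other 21 − z go from 4 to 3. The formula uses only the latter: 100 × (3 − 4)/4 = -25%, as both mean and median. Mean absolute change in all 21 is (3 × z/3 − (21 − z))/21 = (2z − 21)/21.

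| z at 0 | n used by the formula | % change | Mean absolute change, all 21 |
|---|---|---|---|
| 3 | 18 | -25% | -15/21 = -0.71 |
| 6 | 15 | -25% | -9/21 = -0.43 |
| 9 | 12 | -25% | -3/21 = -0.14 |
| 12 | 9 | -25% | +3/21 = +0.14 |

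Because z must be a multiple of 3 here, the sign first reverses at z = 12. With larger worsening it reverses sooner: if 7 subjects go from 0 to 5 and 14 go from 4 to 2, the formula gives -50% on n = 14, while mean absolute change is (35 − 28)/21 = +0.33.

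**Effect of low baselines (assumed data).** Fourteen subjects go from 5 to 4 (-20% each) and two from 1 to 4 (+300% each).

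- Mean % change = (2 × 300 − 14 × 20)/16 = +20%.
- SD = √((2 × 280² + 14 × 40²)/15) = 109.3.
- Median = -20%.
- Mean absolute change = (2 × 3 − 14 × 1)/16 = -0.5.

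Here the mean percentage change shows worsening while the average score improves, the opposite error to the zero-baseline examples.

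**The case against.** The strongest reply is that the subjects leave only a percentage-change column, not the item reporting as a whole. Appendix A gives the TSS separate tables for score and percentage change, whereas the item table's title follows the score pattern. If Table 2.2.3.5 shows scores by visit, every 0 and every rise from 0 is visible, and its n would explain much of any gap in the percentage-change n. The table shells are in a separate document. The closing sentence of 7.4.4 also looks loosely drafted, since it invokes windows that the section never defines. This stands as far as it goes: a reader might infer that new symptoms vanish from all item reporting, and the document does not support that. But neither 7.4.4 nor the table title commits to raw scores, and 7.4.4 names the formula.

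A reader might also infer that the item summary must overstate improvement. That is not supported either. The zero-baseline examples lean that way, but the low-baseline example goes the other way, and with both kinds of subject present the net direction is unknown.

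The required n and median help only in part. On its own, a smaller n does not separate a zero baseline from a missing visit. The median resists the low-baseline distortion (-20% in the example) but does not bring back omitted subjects. The MFSAF items are not a full substitute, because fatigue, concentration, weight loss and fevers are not among them.

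Finally, banning item percentage change outright would be partly a matter of preference. That is fair, and the fix below does not require it.

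**Conclusion.** The point holds, and it is minor. As written, 7.4.4 applies to single items a formula that is undefined at a permitted baseline value and unstable just above it, with no rule for either case. Any item percentage-change summary will omit subjects without the symptom at baseline and cannot show a new symptom, and its mean can mislead in either direction. That subjects are dropped is an inference: the SAP does not say so, but the value is undefined and nothing replaces it.

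The size cannot be read from the document. The figures above rest on assumed baselines and changes and show what can happen, not what is expected.

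The reach is narrow. A reader might take this as a flaw in the symptom endpoints, but Table 1 names TSS and PGIC, and a new symptom still enters the TSS. Section 3.2 says of everything outside the primary test: "All other statistical analyses are exploratory in nature". The primary sign test and the enrollment-stopping rule are unaffected.

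**What to change.** Replace the last sentence of section 7.4.4 with: *Individual MPN-SAF item scores will be summarized by visit as observed score and as absolute change from baseline in all subjects with both values.* Add a note that Table 2.2.3.5 shows these two quantities.

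If item percentage change is kept, restrict it to subjects with an item baseline above 0, report its n and the number with baseline 0, and do not present it alone. A zero-baseline exclusion rule by itself would document the gap but still leave new symptoms out.

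The cost is one sentence and a table note, with no new data. The downside is that item percentage change is dropped or becomes secondary.

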7.4.5. Patient Global Impression of Change

Patient Global Impression of Change is a 1-question patient-reported evaluation of the degree of symptom improvement received since the start of the study ranging from 1 (very much improved) to 7 (very much worse). The PGIC score will be tabulated and summarized descriptively (mean, standard deviation, etc) by visit.

8. PHARMACOKINETIC ANALYSES

Pharmacokinetic analysis will be conducted by the Incyte pharmacokineticist, and the details of the analysis methodology and results will appear in a separate report.

10. SAFETY AND TOLERABILITY

[Appendix A](#) provides a list of data displays. Shells for data displays are provided in a separate document.

10.1. General Considerations

Summary tables may be replaced with listings when appropriate. For instance, an AE frequency table may be replaced with a listing if it only contains a few unique PTs reported on relatively few subjects.

10.2. Adverse Events

10.2.1. Adverse Event Definitions

A TEAE is any AE either reported for the first time or worsening of a pre-existing event after first dose of study drug. Analysis of AEs (as discussed below) will be limited to TEAEs, but data listings will include all AEs regardless of their timing in relation to study drug administration.

Adverse events will be tabulated by MedDRA PT and SOC. Severity of AEs will be graded using the NCI CTCAE. The CTCAE version 4.03 is used for this study. The CTCAE reporting guidelines and grading details are available on the CTEP website.

The subset of AEs considered by the investigator to be related to study drug will be considered to be treatment-related AEs. If the investigator does not specify the relationship of the AE to study drug, the AE will be considered to be treatment-related. The incidence of AEs and treatment-related AEs will be tabulated. In addition, SAEs will also be tabulated.

Any missing onset date, causality, or severity must be queried for resolution. Unresolved missing causality and severity will be handled according to the following rules:

- An unresolved missing causality will be considered treatment-related.
- An unresolved missing severity will be identified as an unknown severity.

For purposes of analysis, all AEs will be considered TEAEs unless the AE can unequivocally be defined as not treatment emergent.

10.2.2. Adverse Events of Special Interest or Adverse Events of Clinical Interest

Adverse events of special interest include Grade 4 thrombocytopenia, Grade 2 or higher anemia, and Grade 2 or higher hemorrhagic events as measured by CTCAE v4.03. Hemorrhagic events will be defined by the SMQ for Haemorrhage using the narrow definition (excluding laboratory terms). Anemia will be defined by the SMQ for haematopoietic erythropenia using the broad

definition. Thrombocytopenia will be defined by the SMQ for haematopoietic thrombocytopenia using the narrow definition. In addition, laboratory shift tables will be generated based on CTCAE v4.03 criteria for low platelet counts and hemoglobin.

10.2.3. Adverse Event Summaries

An overall summary of AEs by cohort will include:

- Number (%) of subjects reporting any TEAEs
- Number (%) of subjects reporting any SAEs
- Number (%) of subjects reporting any Grade 3 or higher TEAEs
- Number (%) of subjects reporting any TEAEs related to itacitinib
- Number (%) of subjects reporting any TEAEs related to ruxolitinib
- Number (%) of subjects who temporarily interrupted itacitinib because of TEAEs
- Number (%) of subjects who temporarily interrupted ruxolitinib because of TEAEs
- Number (%) of subjects who permanently discontinued itacitinib because of TEAEs
- Number (%) of subjects who permanently discontinued ruxolitinib because of TEAEs
- Number (%) of subjects with itacitinib dose reductions because of TEAEs
- Number (%) of subjects with ruxolitinib dose reductions because of TEAEs
- Number (%) of subjects who had a fatal TEAE
- Number (%) of subjects who withdrew from study because of a TEAE

The following summaries will be produced by MedDRA term:

- Summary of TEAEs by SOC and PT
- Summary of TEAEs by PT in decreasing order of frequency
- Summary of TEAEs by SOC, PT, and maximum severity
- Summary of Grade 3 or higher TEAEs by SOC and PT
- Summary of itacitinib treatment-related AEs by SOC and PT
- Summary of Grade 3 or higher itacitinib treatment-related AEs by SOC and PT
- Summary of itacitinib treatment-related AEs by SOC, PT, and maximum severity
- Summary of ruxolitinib treatment-related AEs by SOC and PT
- Summary of Grade 3 or higher ruxolitinib treatment-related AEs by SOC and PT
- Summary of ruxolitinib treatment-related AEs by SOC, PT, and maximum severity
- Summary of TEAEs with a fatal outcome by SOC and PT
- Summary of treatment-emergent SAEs by SOC and PT
- Summary of treatment-emergent SAEs by PT in descending order of frequency

- Summary of itacitinib treatment-related SAEs by SOC and PT
- Summary of ruxolitinib treatment-related SAEs by SOC and PT
- Summary of TEAEs leading to itacitinib dose reduction by SOC and PT
- Summary of TEAEs leading to ruxolitinib dose reduction by SOC and PT
- Summary of TEAEs leading to itacitinib dose interruption by SOC and PT
- Summary of TEAEs leading to ruxolitinib dose interruption by SOC and PT
- Summary of TEAEs leading to discontinuation of itacitinib by SOC and PT
- Summary of TEAEs leading to discontinuation of ruxolitinib by SOC and PT
- Summary of TEAEs leading to withdrawal from the study by SOC and PT
- Summary of treatment-emergent non-SAE by SOC and PT

10.3. Clinical Laboratory Tests

10.3.1. Laboratory Value Definitions

Laboratory values and change from baseline values will be summarized descriptively by visit. Baseline will be determined according to Section 4.1.3. If there are multiple values that meet the criteria for baseline, additional rules may be provided after consultation with the medical monitor to delineate which value will be defined as baseline.

Laboratory test values outside the normal range will be assessed for severity based on CTCAE grade or similar criteria where clinical intervention is required for CTCAE grading. The incidence of abnormal laboratory values and shift tables relative to baseline will be tabulated.

10.3.2. Laboratory Value Summaries

All test results and associated normal ranges from central laboratories will be reported in SI units. All tests with numeric values will have a unique unit per test. Any laboratory test results and associated normal ranges from local laboratories will be converted to SI units. For the limited number of cases where the associated normal ranges from a local laboratory cannot be obtained despite due diligence, a set of standard normal ranges based on documented reference ranges will be applied to facilitate reporting the test results.

When there are multiple laboratory nonmissing values for a subject's particular test within a visit window, the convention described in [Table 3](#) will be used to determine the record used for by-visit tabulations and summaries.

Table 3: Identification of Records for Postbaseline By-Visit Summaries

Priority	Laboratory Visit	Proximity to Visit Window	Tiebreaker
1	Scheduled	In-window	Use smallest laboratory sequence number
2	Unscheduled	In-window	
3	Scheduled	Out-of-window	

Numeric laboratory values will be summarized descriptively in SI units, and non-numeric test values will be tabulated when necessary. In addition, line graphs and box-and-whisker plots will be provided for hemoglobin, platelet counts, WBC, and neutrophils.

Shift tables based on worst postbaseline value recorded will use all postbaseline values occurring within 30 days of stopping study treatment. Shift summaries will be produced for each test for the safety population. The denominator for the percentage calculation will use the number of subjects in the baseline category (ie, low, high, normal, missing) as the denominator for the percentage in each of the categories during the treatment period.

Shift tables will be presented showing change in CTCAE grade from baseline to worst grade postbaseline. Separate summaries for abnormally high and abnormally low laboratory values will be provided when the laboratory parameter has both high and low grading criteria. The denominator for the percentage calculation will be the number of subjects in the baseline category.

